15.6.4 Pregnancy Test

Pregnancy testing (serum β -HCG) will be performed at screening and 30 days post-treatment. A listing will display all the results as presented in “Pregnancy Test” eCRF page.

16 Analyses of Other Endpoints

16.1 Pharmacokinetics

Population: PK analysis set

Non-compartmental computation of PK parameters will be performed using the computer program Phoenix® WinNonlin® version 6.4, or higher (Pharsight Corporation, a Certara Company, Princeton, New Jersey). The statistical software SAS® (Statistical Analysis System, SAS-Institute, Cary North Carolina), Windows version 9.2 or higher will be used to produce tables, listings and figures. Figures will be prepared with SAS Version 9.2, or higher.

Pharmacokinetic parameters will be calculated using standard non-compartmental methods and the actual administered dose.

For each subject with PK data, the following PK parameters will be calculated for M3814 and **CCI** as either single or multiple dose, as follows and as appropriate.

- FD1 – single dose
- **CCI** – single dose if it occurs on a Monday
- All other fraction days - multiple dose.

C_{max} Maximum observed concentration

$C_{max}/Dose$ The Dose-normalized maximum observed concentration. Normalized using the actual dose, and the formula $C_{max}/Dose$.

AUC_{0-4} Area under the concentration-time curve (AUC) from time zero to time 4 hours postdose. AUC_{0-4} will be based on the estimated concentration at 4 hours and not the concentration at the actual observation time. For **CCI** in case no regression is available and a sample has been collected at 4 hours within the protocol-defined collection window (3.5 to 4.5 hours), actual time may be used.

$AUC_{0-4}/Dose$ The Dose-normalized AUC from time zero to 4 hours postdose. Normalized using the actual dose, using the formula $AUC_{0-4}/Dose$.

AUC_{0-6} Area under the concentration-time curve (AUC) from time zero to time 6 hours postdose. AUC_{0-6} will be based on the estimated concentration at 6 hours and not the concentration at the actual observation time. In case no regression is available and a sample has been collected at 6 hours within the protocol-defined collection window (5.5 to 6.5 hours), actual time may be used.

$AUC_{0-6}/Dose$ The Dose-normalized AUC from time zero to 6 hours postdose. Normalized using the actual dose, using the formula $AUC_{0-6}/Dose$.

AUC ₀₋₁₂	Area under the concentration-time curve (AUC) from time zero to time 12 hours postdose. AUC ₀₋₁₂ will be based on the estimated concentration at 12 hours based on the elimination rate constant.
AUC ₀₋₁₂ /Dose	The Dose-normalized AUC from time zero to 12 hours postdose. Normalized using the actual dose, using the formula AUC ₀₋₁₂ /Dose.
t _{max}	Time to reach the maximum observed concentration C _{max}
t _{last}	The last sampling time at which the concentration is at or above the lower limit of quantification (LLOQ).
R _{acc(Cmax)}	Accumulation ratio for C _{max} , calculated as C _{max} CCI C _{max,FD1} (all dose groups)
F _{rel(Cmax)}	Relative bioavailability for C _{max} of tablet compared to capsule formulation C _{max,FD1} /C _{max} C (tablet testing group only)
R _{acc(AUC0-4)}	Accumulation ratio for AUC ₀₋₄ calculated as AUC ₀₋₄ CCI AUC _{0-4,FD1} (all dose groups)
F _{rel(AUC0-4)}	Relative bioavailability for AUC ₀₋₄ of tablet compared to capsule formulation AUC _{0-4,FD1} /AUC ₀₋₄ C (tablet testing group only)
R _{acc(AUC0-6)}	Accumulation ratio for AUC ₀₋₆ calculated as AUC ₀₋₆ CCI AUC _{0-6,FD1} (all dose groups)
R _{acc(AUC0-12)}	Accumulation ratio for AUC ₀₋₁₂ calculated as AUC ₀₋₁₂ CCI AUC _{0-12,FD1} (all dose groups)
R _{acc(AUC0-24)}	Accumulation ratio for AUC ₀₋₂₄ calculated as AUC ₀₋₂₄ CCI AUC _{0-24,FD1} (all dose groups)
F _{rel(AUC0-24)}	Relative bioavailability for AUC ₀₋₂₄ of tablet compared to capsule formulation AUC _{0-24,FD1} / AUC ₀₋₂₄ C (tablet testing group only)
AUC ₀₋₂₄	Area under the concentration-time curve (AUC) from time zero to time 24 hours. AUC _{0-24h} will be calculated after the first dose on Fraction Day 1 and after dosing on Fraction Day 6 (in tablet testing group only) and Fraction Day 10. AUC ₀₋₂₄ will be based on the estimated concentration at 24 hours, and not the concentration at the actual observation time. For FD1 and CCI in case no regression is available and a sample has been collected at 24 hours within the protocol-defined collection window (23.5 to 24.5 hours), actual time may be used. For CCI where available, the pre-dose concentration will be duplicated and used as the 24 hour concentration to allow AUC ₀₋₂₄ to be calculated (assuming steady state after multiple dosing).
AUC ₀₋₂₄ /Dose	The Dose-normalized AUC from time zero to 24 hours. Normalized using the actual dose, using the formula AUC ₀₋₂₄ /Dose.

$C_{av,0-24}$	Average concentration from time zero to 24 hours. Formula: $AUC_{0-24}/24$.
$AUC_{0-\infty}$	The AUC from time zero (dosing time) extrapolated to infinity, based on the predicted value for the concentration at t_{last} , as estimated using the linear regression from λ_z determination. $AUC_{0-\infty}=AUC_{0-t}+C_{last\ pred}/\lambda_z$; FD1, CCI (tablet testing group), single dose data.
$AUC_{0-\infty}/\text{Dose}$	The Dose-normalized AUC from time zero extrapolated to infinity. Normalized using actual dose, and the formula $AUC_{0-\infty}/\text{Dose}$; FD1, CCI (tablet testing group), single dose data.
$t_{1/2}$	Apparent terminal half-life, $t_{1/2} = \ln 2/\lambda_z$, where λ_z is defined as the terminal first order elimination rate constant
CL/f	Apparent total body predicted clearance of drug, calculated by $\text{Dose}/AUC_{0-\infty}$. FD1, CCI (tablet testing group), M3814 only.
V_z/f	Apparent predicted volume of distribution during the terminal phase. $V_z/f = \text{Dose}/(AUC_{0-\infty} \cdot \lambda_z)$ FD1, CCI (tablet testing group), M3814 only.
C_{trough}	Trough Concentration; predose concentration on FD2, CCI FD7 and CCI
CCI	

The following PK parameters will be calculated for diagnostic purposes and listed, but will not be summarized:

- Percentage of $AUC_{0-\infty}$ obtained by extrapolation (AUC_{extra}), calculated by $(1-[AUC_{0-t}/AUC_{0-\infty}]) \times 100$.
- The time interval (h) of the log-linear regression to determine λ_z .
- Number of data points included in the log-linear regression analysis to determine λ_z .
- Goodness of fit statistic (Rsq,adj) for calculation of λ_z .

Plasma PK concentrations for M3814 and **CCI** will be listed and summarized by group (e.g. dose level, fraction day, analyte) using standard descriptive statistics. A listing of PK blood sample collection times as well as derived sampling time deviations will also be provided.

Individual concentration-time profiles showing all subjects by dose level, analyte and fraction day and profiles showing all subjects using the entire time course by dose level, analyte and formulation group will be created using the actual time points and the numeric concentration data. Arithmetic mean concentration-time profiles by group will be provided using scheduled (nominal)

time points and the numeric concentration data. All concentration-time plots for PK data will be presented both on a linear and on a semi-logarithmic scale. Mean plots will include SD error bars when plotted on a linear scale.

The trough concentrations (C_{trough}) for FD2, **CCI** FD7, and **CCI** will be listed and summarized by group (e.g. dose level, fraction day, analyte), using standard descriptive statistics. Individual C_{trough} values will be plotted against actual time points on a linear scale, for all subjects by dose level. Arithmetic mean $C_{trough} \pm SD$ will also be plotted by dose level, on a linear scale.

The calculation of the AUC will be performed using the mixed log-linear trapezoidal method. The actual time of blood sampling will be used for PK parameter calculation. In cases where the actual sampling time is missing, calculations will be performed using the scheduled time.

Partial areas AUC_{0-4} AUC_{0-6} , AUC_{0-12} , and AUC_{0-24} should be calculated using the scheduled dosing interval. The actual interval calculated from CRF time data should not be used.

Pre-dose samples will be considered as if they had been taken simultaneously with the administration, and will be assigned a time of 0 hours. Concentrations below the lower limit of quantification (LLOQ), will be taken as zero for summary statistics of PK concentration data, NCA and for graphical presentations.

The regression analysis should contain data from at least 3 different time points in the terminal phase consistent with the assessment of a straight line on the log-transformed scale. Phoenix WinNonlin “best fit” methodology will be used as standard. However, in some cases, further adjustment may be made by the pharmacokineticist, if warranted, after agreement with the Sponsor. The last quantifiable concentration should always be included in the regression analysis, while the concentration at t_{max} and any concentrations below LLOQ which occur after the last quantifiable data point should not be used.

[figure not shown]
AUC_{extra} should not be greater than 20%, the coefficient of correlation (R^2) should be ≥ 0.8000 and the observation period over which the regression line is estimated should be at least twofold the resulting $t_{1/2}$ itself. If these criteria are not met, then the rate constants and all derived parameters (e.g. CL/f , and Vz/f etc.) will be included in the parameter outputs and descriptive statistics but will be flagged and discussed appropriately. Any flags will be included in the study specific SDTM/ADaM.

Scatter plots and box plots of individual dose-normalized C_{max} , C_{av0-24} , AUC_{0-4} , AUC_{0-6} , AUC_{0-12} , AUC_{0-24} , and $AUC_{0-\infty}$ values versus dose will be presented graphically.

All descriptive summaries of PK data will be performed using the PK Analysis Set. Individual PK data will be listed using the Safety Analysis Set. The mean concentration-time profiles and PK parameter plots will be plotted using the PK Analysis Set and the individual subject concentration-time profiles will use the Safety Analysis Set. Exploratory dose proportionality analysis will be performed by visual inspection of the scatter plots and box plots of $C_{max}/dose$ and $AUC_{0-4}/dose$ against dose.

The Phoenix WinNonlin NCA Core Output will be provided in a separate listing.

CCI

CONFIDENTIAL
INFORMATION

46/60

CCI

17

References

CONFIDENTIAL
INFORMATION

47/60

18 Appendices

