Table 9 Pharmacokinetic and **CCI** Sampling Schedule of M3814 during Phase Ia, Phase Ib, and the Ancillary cPoP Part of the Trial

	Time points Volume of blood required per time point ^a	Phase Ia		Phase Ib ^b		Ancillary cPoP	
		PK ^c 2 mL	CCI	PK ^c 2 mL	CCI	PK ^c 2 mL	CCI
FD 1	Predose	X		X			
	H 0.5	X		X			
	H 1.0	X					
RT	1.5 hours (± 30 minutes) after dosing	3 Gy x 10; 5 2 Gy x 33-35;		2 Gy x 33; 5 2 Gy x 33-35; 5		10-25	
	H 2.0	X		X			
	H 4.0	X		X			
	H 6.0	X		X			
FD 2	Predose ^d	X				X	
	H 0.5					X	
	H 1.0					X	
RT	1.5 hours (± 30 minutes) after dosing	3 Gy x 10; 5 2 Gy x 33-35;		2 Gy x 33; 5 2 Gy x 33-35; 5		10-25	
	H 2.0					X	
	H 4.0					X	
FD 6	Predose ^d	X					
	H 0.5 ^g	X					
	H 1.0 ^g	X					
RT	1.5 hours (± 30 minutes) after dosing	3 Gy x 10; 5 2 Gy x 33-35;		2 Gy x 33; 5 2 Gy x 33-35; 5			
	H 2.0 ^g	X					
	H 4.0 ^g	X					
	H 6.0 ^g	X					
FD 7^g	Predose ^d	X					
FD 10^f	Predose ^d	X		X			
	H 0.5	X		X			
	H 1.0	X					
RT	1.5 hours (± 30 minutes) after dosing	3 Gy x 10; 5 2 Gy x 33-35;		2 Gy x 33; 5 2 Gy x 33-35; 5			
	H 2.0	X		X			
	H 4.0	X		X			

cPoP = clinical proof-of-principle; FD = fraction day; F/W = fraction per week; Gy = Gray; NSCLC = non-small cell lung cancer; **CCI** ; PK = pharmacokinetic; RT = radiotherapy; SCCHN = squamous cell carcinoma head and neck; SMC = Safety Monitoring Committee.

[figure not shown]
- a Pharmacokinetic sampling should be performed within \pm 15 minutes of the first 30 minute postdose sample collections, and within \pm 30 minutes for subsequent sampling at each sampling day. The predose sample should be taken within 1 hour before dosing at each sampling day.
- b PK and CCI sampling for the first 3 subjects in Phase Ib (NSCLC expansion cohort) will follow the same schedule as for Phase Ia, as shown in this table.

CCI

- d For the purpose of PK parameter calculations, the predose value will also serve as an estimate for the 24-hour postdose concentrations of the previous FD.
- e The blood sample closest in time to the biopsy should be collected as close as possible to the time of the biopsy.
- f If FD 10 is on a Friday, PK and CCI sampling must be done on FD 9.
- g Only for patients treated in the tablet testing cohorts in Phase Ia Arm A.

CCI

2

Sponsor, Investigators and Trial Administrative Structure

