6.2 Final Analysis

Cut-off date:

All final, planned analyses identified in the Clinical Trial Protocol and in this IAP will be performed only after the last subject has completed one year of follow-up, all data queries resolved, and the database locked.

A data review meeting will be held prior to database lock. In addition, no database can be locked until this IAP has been approved.

7

Changes to the Planned Analyses in the Clinical Trial Protocol

The protocol specifies the following PK parameters to be reported for Fraction Day 10: CLss/f, Vss/f, AUC_{0-t}, and AUC_t. These will not be calculated or reported due to the limited number of PK samples to be collected in the terminal phase leading to unreliable parameter estimates, please refer to Section 16.1 for a complete list of PK parameters which will be reported. In addition, standard error of the mean will not be a descriptive statistic used to describe PK variables.

In section 8.5.4.3 of the protocol the following analysis is described regarding data coming from the physical examination: "Data will be further analyzed using concentration effect modeling for baseline-corrected QTcF values obtained at Day 1." This analysis will not be performed so will not be included in this analysis plan.

In the protocol a number of biomarker analysis sets are defined. These will not be used and instead the SAF analysis set will be used for biomarker analyses.

7.1

COVID-19 Impact

Additional listings will be generated to assess potential impacts of COVID-19 to this study including:

- listing of participants potentially affected by pandemic and with any AEs or PDs related to COVID-19
- listing of PDs related to COVID-19
- listing of AEs related to COVID-19.

8

Protocol Deviations and Analysis Sets

8.1

Definition of Protocol Deviations and Analysis Sets

Important protocol deviations are protocol deviations that might significantly affect the completeness, accuracy, and/or reliability of the study data or that might significantly affect a subject's rights, safety, or well-being.

Important protocol deviations will be categorized in to one of the following:

- Subject enrolled and dosed on the study who did not satisfy enrolment criteria
- Subject fulfills withdrawal criteria whilst on the study but is not withdrawn
- Subject is administered the wrong treatment or an incorrect dose
- Subject is administered or takes concomitant medication excluded by the CTP

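### The SAP's duplicated 24 h concentration has no visible check on time since the previous dose, so a Monday FD10 would receive a value about 72 h old

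*SAP*

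**What the plan says.** SAP Section 16.1 defines AUC0-24 for FD1, for FD6 ("in tablet testing group only) and Fraction Day 10" completes the list), and describes two sources for the concentration at 24 h.

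- For FD1 and one redacted day, if no regression is available, a real sample may be used when it falls "within the protocol-defined collection window (23.5 to 24.5 hours), actual time may be used".
- For another redacted day, where a predose value exists, "the pre-dose concentration will be duplicated and used as the 24 hour concentration". The stated justification is steady state after multiple dosing.

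The same section sorts days into single and multiple dose. FD1 is single dose. A redacted day is "single dose if it occurs on a Monday". Then: "All other fraction days - multiple dose".

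The protocol uses predose samples differently. In Table 9, footnote d, "the predose value will also serve as an estimate for the 24-hour postdose concentrations of the previous FD". That rule assigns the sample to the day before; the SAP's duplication assigns it to the 24 h still to come.

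On the calendar, RT and M3814 are given five times a week with no weekend dosing. The protocol moves PK sampling to FD9 if FD10 is a Friday. For the tablet cohorts it places FD6 on a Monday. It has no visible rule for an FD10 that falls on a Monday.

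**The concern.** The predose value can stand in for the 24 h value only if two successive dosing intervals look alike. On a Monday that fails: the predose sample reflects a weekend without drug, while the next 24 h follow a fresh dose.

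The borrowed value is small, but it matters. The last FD10 sample listed in Table 9 is at 4 h, so one number fixes the shape of the curve over the remaining 20 h. If it is wrong, AUC0-24, its dose-normalised form, Cav,0-24 and Racc(AUC0-24) are wrong with it. Dose-escalation cohorts have 3 subjects, so one affected subject can shift a dose-level summary. Racc for AUC is a secondary PK endpoint in protocol Section 8.3.2.3.

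**Working it through.** The documents give no AUC figure to reproduce, so the check covers which day is meant, whether the calendar allows the case, and the size of the error.

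**Which day.** FD1 has a next-day sample (FD2 predose), and tablet FD6 has one (FD7 predose). FD10 has none. By elimination, and from the steady-state wording, the duplication day is FD10 (or FD9 when sampling is moved). This is an inference.

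**Calendar.** At five fractions a week without interruption:

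| FD1 | FD10 | PK sampling day | Previous dose |
|---|---|---|---|
| Mon | Fri | FD9, Thu | 24 h earlier |
| Tue | Mon | FD10, Mon | 72 h earlier |
| Wed | Tue | FD10, Tue | 24 h earlier |
| Thu | Wed | FD10, Wed | 24 h earlier |
| Fri | Thu | FD10, Thu | 24 h earlier |

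Protocol Section 7.5.2.1 expects that some subjects will not start on a Monday. A Monday start with one missed fraction also moves FD10 to a Monday, since Section 6.6.3 puts missed fractions at the end.

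**Inputs from the documents.** Half-life 5.5 h, range 2.0 to 8.8 h (protocol Section 5.2); mixed log-linear trapezoid; values below LLOQ set to zero in the noncompartmental analysis (both SAP 16.1).

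**Assumptions.** One compartment; ka 0.8, 1.5 and 3.0 per h; last sample at 4 h or, as a variant, 6 h. LLOQ is not given, so both cases are shown. A zero is assumed to enter the profile as a 24 h point.

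**The 4 to 24 h segment alone.** Take C4 = 1 and k = ln 2 / 5.5 = 0.126 per h.

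- True value: C24 = exp(−20k) = 0.080; area = (1 − 0.080)/k = 7.30.
- 72 h value used as C24: exp(−68k) = 1.9 × 10⁻⁴; log-trapezoid area = 20 × (1 − 0.00019)/ln(1/0.00019) = 2.33. Error 2.33/7.30 − 1 = −68%.
- Zero used as C24 (linear rule): 20 × (1 + 0)/2 = 10.0. Error 10.0/7.30 − 1 = +37%.

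**Whole AUC0-24.** Single-dose profile C(t) = ka/(ka − k) × [exp(−kt) − exp(−ka t)], summed over Tuesday-start doses on days 0, 1, 2, 3, 6, 7, 8, 9, 10 and 13, with half-life 5.5 h. The true Racc(AUC0-24) is 1.00 because the weekend removes accumulation.

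| ka | Last sample | Error, true C24 | Error, 72 h value | Error, zero | Racc, 72 h value | Racc, zero |
|---|---|---|---|---|---|---|
| 0.8 | 4 h | −3.4% | −48.9% | +19.3% | 0.52 | 1.21 |
| 0.8 | 6 h | −1.5% | −37.9% | +12.0% | 0.63 | 1.14 |
| 1.5 | 4 h | −1.0% | −44.4% | +22.5% | 0.56 | 1.24 |
| 1.5 | 6 h | −0.9% | −34.6% | +12.0% | 0.66 | 1.13 |
| 3.0 | 4 h | −0.9% | −42.4% | +21.7% | 0.58 | 1.23 |
| 3.0 | 6 h | −0.9% | −33.1% | +11.3% | 0.68 | 1.12 |

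For a Tuesday FD10 (Wednesday start), the same duplication errs by only about −2% to −4%.

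**Other half-lives.** At 8.8 h the quantifiable case gives −37% to −49% and the zero case −1% to −6%. At 2.0 h the zero case gives +28% to +85%. The quantifiable case is not credible there, since 72 h is 36 half-lives.

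**The case against.** The strongest reply is that the decisive words are redacted. The duplication day is blacked out, and so is the day in the Monday rule. If the Monday rule includes FD10, a Monday FD10 is already treated as single dose. The duplication is also tied to steady state, which a careful programmer might take as excluding a Monday.

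This stands as a limit on certainty. FD6 is the likelier subject of the Monday rule: the protocol moves it to a Monday for wash-out, and the single-dose parameters are listed for FD1 and a redacted day in the tablet group. FD10 would then fall under the multiple-dose line. The visible text does not settle it, and steady state is stated there as an assumption without an interval check.

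The direction of error is also open. At 5.5 h the 72 h predose is about 0.015% to 0.020% of single-dose Cmax, so it is quantifiable only with an LLOQ below that.

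Four stronger readings are tempting and are not supported.

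- **The error reaches tablet-capsule bridging or dose choice.** The formulation comparison uses FD1 against FD6. Outputs for the SMC come from a separate analysis plan. The DLT analysis uses no PK, and the dose-proportionality inspection names Cmax/dose and AUC0-4/dose.
- **FD10 AUC0-24 should go altogether.** SAP Section 7 drops AUCtau "due to the limited number of PK samples to be collected in the terminal phase leading to unreliable parameter estimates", and for once-daily dosing AUC0-24 is the same quantity. But duplication is the workaround for sparse sampling, and it performs well when the previous dose was 24 h earlier.
- **The FD10 regression cannot meet the SAP's criteria, so failing values should be listed only.** The SAP does not say whether the duplicated point enters the regression. If it does, points at 2, 4 and 24 h span 22 h and satisfy the twofold rule up to a half-life of 11 h. Results that fail "will be included in the parameter outputs and descriptive statistics but will be flagged and discussed appropriately", which is a stated choice.
- **One subject in five is affected.** That needs evenly spread start days, which no section supports.

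**Conclusion.** The point holds conditionally. If the duplication applies to FD10, as is most likely, and the redacted Monday rule does not cover FD10, a subject sampled on a Monday FD10 gets a materially wrong AUC0-24, with AUC0-24/Dose, Cav,0-24 and Racc(AUC0-24) following it. At the 5.5 h half-life the error is about −33% to −49% or +11% to +23%, depending on whether the predose value is quantifiable, against about −1% to −3% with the true 24 h concentration. Racc(AUC0-24) would read 0.52 to 0.68 or 1.12 to 1.24 where 1.00 is right. These sizes rest on the one-compartment model, the assumed ka range and the unknown LLOQ.

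The reach is limited to descriptive secondary PK in the trial report, including the plots of dose-normalised AUC0-24 and Cav,0-24 against dose. The share of subjects affected cannot be derived from the documents. Cmax, AUC0-4 and their accumulation ratios need no 24 h value. The clarification is worth making because it is cheap and the error is large where it occurs.

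**What to change.** Add one condition to the AUC0-24 definition in SAP 16.1: the predose concentration is duplicated as the 24 h value only if the previous M3814 dose was about 24 h before that sample. The 23.5 to 24.5 h window already in the section could serve. Because the protocol lets the predose sample be taken up to 1 h before dosing, a somewhat wider window would avoid losing ordinary weekday samples and would still exclude a weekend gap.

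In all other cases, including a Monday FD10, either use a flagged 24 h value extrapolated from that day's own profile, or leave AUC0-24, AUC0-24/Dose, Cav,0-24 and Racc(AUC0-24) for that day out of the summaries. An extrapolated value rests on few late samples, hence the flag. If the redacted Monday rule already covers FD10, a cross-reference from the AUC0-24 definition is enough.

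The cost is a line in the SAP and a date check in the program; protocol Section 7.5.1 already requires drug administration and exact sampling times to be recorded. The downside is that slightly fewer subjects contribute an FD10 AUC0-24.

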- y. Subjects treated in the tablet testing cohorts of Phase Ia Arm A will receive the tablet on FD 1-5 and FD 7-10 and a respective single dose strength of the capsule formulation on FD 6.

- z. If FD6 is NOT on a Monday then it must be scheduled to take place on the Monday closest to FD6 as wash-out over the weekend is required.
- aa. PTD 210 and 312 will consist of phone calls to evaluate long term RT toxicity. No other assessments will be performed at these visits.

Table 3 Schedule of Assessments – First 3 Subjects in Phase Ib (Arm A; NSCLC Cohort)

Trial Periods	Screening	DLT Evaluation Period						DLT Period/Short-term Safety FU	Mid-term Safety FU	Long-term Safety FU/ EOT ^a	Survival FU
		Treatment Period (M3814 + RT)									
Trial Days	Day -21 to Day -1	FD 1 to FD 33						PTD 1 to 37	PTD 1 to 90	PTD 31 to 365	-
M3814 RT 2 Gy x 33 (5 F/W) ^b		X X									
Visit Days	-21 to -1	FD 1	FD 2	FD 6	FD 10 ^c	FD 16, 21, 26 and 33/ETT ^d	PTD 8, 15, 22, 37 ^e	PTD 84	PTD 42, 126, 168, 180, 210 ^x , 270, 312 ^x , and 365	-	-
Visit Window (days)	-	-	-	-	-	-	±2	±7	±7	-	-
Signed informed consent	X										
Inclusion/exclusion criteria	X	X									
Demography	X										
Medical history	X										
Serum β-HCG pregnancy test (if applicable)	X						PTD 22 only				
Infection screen (hepatitis B and C), optional HIV test ^f	X										
Vital signs ^g	X ^h	X		X	X	X	X	X	X		
Physical examination	X	X		X	X	X	X	X	X ⁱ		
Clinical examination of bleeding	X	X		X	X	X	X				

Trial Periods	Screening	DLT Evaluation Period						DLT Period/Short-term Safety FU	Mid-term Safety FU	Long-term Safety FU/ EOT ^a	Survival FU
		Treatment Period (M3814 + RT)									
Trial Days	Day -21 to Day -1	FD 1 to FD 33						PTD 1 to 37	PTD 1 to 90	PTD 31 to 365	-
M3814 RT 2 Gy x 33 (5 F/W) ^b		X X									
Visit Days	-21 to -1	FD 1	FD 2	FD 6	FD 10 ^c	FD 16, 21, 26 and 33/ETT ^d	PTD 8, 15, 22, 37 ^e	PTD 84	PTD 42, 126, 168, 180, 210 ^x , 270, 312 ^x , and 365		-
Visit Window (days)	-	-	-	-	-	-	±2	±7	±7		-
Esophageal endoscopy (if relevant)	X										
Evaluation of all tissues in RT area				X	X	X	X	X	X		
ECOG PS	X				X	FD 33 only	X	X	X		
Adverse event assessment	X	X		X	X	X	X	X ^f	X ^f		
Concomitant medication	X	X		X	X	X	X				
Hematology ^k	X	X		X	X	X	X				
Serum chemistry and coagulation ^l	X	X		X	X	X	X				
Urinalysis (dipstick) ^m	X				X	FD 16 and 33 only	X				
12-lead ECG (including QTcF) ⁿ	X	X ^o			X ^p						
Tumor assessment (RECIST) ^{q, r}	X							X	X		
PK blood samples ^s		X	X ^t	X	X						

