After review of the safety, tolerability, and PK data from this cohort in relation to the data obtained in the ongoing dose escalation, the SMC may decide to test further tablet dose levels. The aim is to confirm the RP2D that has been defined for the capsule, using the tablet formulation.

The design of the tablet testing cohorts in the Phase Ia part of Arm A also includes intra-individual comparison of single dose PK of M3814 after administration of the tablet versus capsule. The capsule administered on FD6 after a 48-hour wash-out is not expected to be influenced by the previous administration of M3814 tablets on FD1 to FD5, considering the median terminal half-life of 5.5 hours (range 2.0 to 8.8 hours, preliminary data estimated in the **CCI** [REDACTED]) after multiple daily dosing. Clinical safety, tolerability, and PK results obtained in Phase Ia Arm A will determine subsequent introduction of the tablet in other parts of the trial.

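### The trough definition in SAP 16.1 shows no condition on time since the previous dose, so predose samples taken after a weekend (about 72 h post-dose) would be summarised as troughs

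*SAP*

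**What the plan says.** SAP 16.1 gives the definition "Trough Concentration; predose concentration on FD2", followed by a blacked-out entry, FD7 and a second blacked-out entry. The same four days recur where the output is described: the troughs "will be listed and summarized by group (e.g. dose level, fraction day, analyte), using standard descriptive statistics". Individual "values will be plotted against actual time points on a linear scale, for all subjects by dose level", and arithmetic mean troughs with SD are plotted by dose level. Neither place shows a limit on the time since the previous dose.

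Protocol Table 9 schedules Phase Ia predose samples after FD1 on FD2, FD6, FD7 and FD10 only, with FD7 restricted to the tablet cohorts of Arm A. FD10 sampling moves to FD9 when FD10 is a Friday. Footnote d to that table takes a predose value as an estimate of the 24 h concentration of the previous fraction day.

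In the tablet cohorts a capsule replaces the tablet on FD6 (Table 2, footnote y). Footnote z says that when FD6 is not a Monday "it must be scheduled to take place on the Monday closest to FD6 as wash-out over the weekend is required". Protocol 5.2 adds: "The capsule administered on FD6 after a 48-hour wash-out is not expected to be influenced", citing a "median terminal half-life of 5.5 hours (range 2.0 to 8.8 hours").

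SAP section 9 presents data by arm, formulation and dose level, and pools cohorts that share a dose level.

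**The concern.** A trough at once-daily dosing is the concentration about 24 h after the previous dose. A fraction day does not fix that interval when dosing stops at weekends: the same fraction day can be 24 h or 72 h after the last dose, depending on the weekday of FD1.

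Two parts of this can be seen without guessing at the blacked-out text. FD2 is legible, and after a Friday start it falls on a Monday. Protocol 7.5.2.1 expects that some subjects will not start on a Monday, and no visible Phase Ia rule excludes a Friday start. FD7 is also legible. It is sampled only in the tablet cohorts, where the preceding dose is the FD6 capsule, so it is a capsule value shown within a tablet group with no visible label.

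The third part depends on FD6 and FD10 being the hidden days. The FD6 predose sample in the tablet cohorts is then a wash-out check by design, and it would enter the trough table and the mean plot as a trough. What is at stake is the reading of those two outputs: a low mean or a large SD could come from the calendar and not from the drug.

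**Working it through.** **Inputs.** Five fractions per week (protocol 5.1). Half-life 5.5 h, range 2.0 to 8.8 h (protocol 5.2). Predose samples within 1 h before dosing (Table 9, footnote a). Assumptions: mono-exponential decline at the stated half-life, no holidays and no missed fractions.

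**The plan's own figure.** Friday dose to Monday dose is 72 h. Less the usual 24 h interval, 72 − 24 = 48 h, which matches the stated wash-out if that means the additional dose-free time. The carry-over statement also holds. At 5.5 h, 72/5.5 = 13.1 half-lives leave about 0.01% of the extrapolated time-zero level. At 8.8 h, 72/8.8 = 8.2 half-lives leave about 0.34%.

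**Hours since the previous dose at the predose sample** (capsule cohorts and Arm B):

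| FD1 weekday | FD2 | FD6 | FD10 (or FD9) |
|---|---|---|---|
| Monday | 24 | 72 | 24 (FD9, a Thursday) |
| Tuesday | 24 | 24 | 72 |
| Wednesday | 24 | 24 | 24 |
| Thursday | 24 | 24 | 24 |
| Friday | 72 | 24 | 24 |

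In the tablet cohorts FD6 is always a Monday, so its predose sample is always about 72 h after the last tablet. FD7 is then a Tuesday, 24 h after the capsule.

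**Size of a 72 h value relative to a 24 h trough**, 2^−((72 − 24)/t½):
- t½ = 5.5 h: 2^−8.73 = 0.0024, or 0.24% (1/424).
- t½ = 8.8 h: 2^−5.45 = 0.0228, or 2.3% (1/44).
- t½ = 2.0 h: 2^−24, about 0.000006%. Here the 24 h value is itself 12 half-lives after dosing (about 0.02% left), so the comparison says little.

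**Effect on a group mean.** Set every true 24 h trough to 1 and let k of n subjects contribute a 72 h value r. The mean is ((n − k) + k·r)/n.
- n = 3, k = 1: (2 + 0.0024)/3 = 66.7% at 5.5 h, with CV 86%; 67.4% at 8.8 h, with CV 84%.
- n = 3, k = 2: 33.5% at 5.5 h and 34.9% at 8.8 h.
- n = 6, k = 1: 83.4% at 5.5 h and 83.7% at 8.8 h.
- n = 6, k = 3: 50.1% at 5.5 h and 51.1% at 8.8 h.
- All subjects at 72 h (tablet-cohort FD6): 0.24% at 5.5 h and 2.3% at 8.8 h.

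The CVs given arise from the timing alone, because the true troughs were set equal.

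**The case against.** The strongest objection is that FD6 and FD10 cannot be read in the Ctrough definition, and a blacked-out qualifier tied to weekday or cohort cannot be excluded. The authors knew of the weekend gap. The same section treats one blacked-out day as single-dose if it falls on a Monday, and accepts an actual 24 h sample for AUC0-24 only within 23.5 to 24.5 h. This objection stands as a limit on certainty: Table 9 makes the hidden days very probable, not proven. It does not touch FD2 or FD7.

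Secondly, a near-zero FD6 value in the tablet cohorts is what the design intends, and those values are uniform. A reader might infer that the tablet groups mix 24 h and 72 h values on FD6. They do not, and section 9 keeps tablet and capsule apart by default. The tablet FD6 fault is one of labelling; FD6 blending arises in the capsule and Arm B groups.

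Thirdly, safeguards exist. Individual troughs are plotted against actual time, and sampling times with their deviations are listed. A careful PK reader could identify the weekend values, but the summary table and mean plot show no exclusion or flag.

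Fourthly, no visible decision rests on Ctrough. PK is descriptive, with any tests exploratory (protocol 8.5.3.1.1). For tablet dose decisions, protocol 5.1.2 names tmax, Cmax and AUC0-24 as examples, and the SMC outputs have their own analysis plan. This stands, and it limits the weight of the point.

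**Conclusion.** The point holds as a defect in a descriptive secondary PK summary. The visible rule would classify weekend-preceded samples as troughs, although they are about 0.2% to 2.3% of a 24 h value at half-lives of 5.5 to 8.8 h. In a group of three, one such value cuts the mean to about 67%. The effect per subject is smaller in larger pooled groups. How often it occurs depends on FD1 weekdays, which the documents do not give. The tablet-cohort FD7 value needs a label whatever the blacked-out days are.

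Three stronger readings are not supported. SAP 16.1 does not count every predose sample as a trough; it lists fraction days. It cannot be said which 72 h values would be set to zero: the rule is that "Concentrations below the lower limit of quantification (LLOQ), will be taken as zero for summary statistics of PK concentration data", but no LLOQ is stated. Nor do the documents show an effect on the DLT endpoint or the dose recommendation.

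The conclusion rests on log-linear decline at the stated half-lives, an uninterrupted five-day schedule and, for FD6 and FD10, the inference from Table 9.

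**What to change.** In SAP 16.1:
- Derive hours since the previous dose for each predose sample. Summarise and plot as Ctrough only samples taken about 24 h after that dose, within a prespecified window set by the sponsor.
- List predose samples that follow a weekend or a missed fraction separately as wash-out concentrations. In the tablet cohorts the FD6 values can then serve to confirm negligible carry-over before the capsule.
- Label the tablet-cohort FD7 value as post-capsule in the table and plots.

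If the blacked-out text already contains such a condition for FD6 or FD10, only FD2 and the FD7 label need attention. The cost is a few lines of SAP text and one derived variable, with no new samples. The downside is a smaller n in some descriptive cells, and no tablet-cohort FD6 trough cell at all.
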